The study is a prospective, randomized, multi-center trial designed to demonstrate the safety and efficacy of the C-Pulse[®] System in relieving heart failure symptoms in patients with ACC/AHA Stage C, NYHA Class III to ambulatory Class IV heart failure. Reduction in heart failure symptoms will be demonstrated by increased freedom from heart failure related hospitalization or death in subjects implanted and treated with the C-Pulse System as compared to a concurrent, randomized control group receiving standard optimal medical therapy (OMT).

Patients will be enrolled into the trial upon providing informed consent. Procedures related directly to the study must not be performed prior to informed consent. Following confirmation of subject eligibility, subjects will be randomized to one of two treatment arms, Treatment or Control, in a 1:1 allocation utilizing a random permuted block design stratified by study center. The Treatment group subjects will receive the C-Pulse[®] System with immediate therapy following implant and OMT while the Control group will continue on OMT. The subjects will not be allowed to cross-over from the assigned group (i.e. a control will not be allowed to receive a C-Pulse). If a treatment subject is explanted, it will be reported in the study analysis per the statistical methods section.

This study will include up to 40 centers in the US and potentially some Canadian centers. The study population will include 388 patients. All subjects who meet eligibility requirements and sign study consent will then be randomized following the baseline testing completion. The follow-up period will be for a minimum of 12 months to assess the safety and efficacy. To facilitate the analysis of the therapeutic effect, it is desired that the system be used all the time. The subject must limit disconnection to a minimal amount of time allowed for personal convenience such as hygiene. The Driver logs subject usage automatically and stores this usage into the system files.

Subjects will be followed for up to five years.

If a subject undergoes anesthesia for the purpose of C-Pulse implantation but does not receive a C-Pulse System, the subject will be followed for 30 days for safety or until they are discharged, whichever occurs first.

[figure not shown]

Figure 1. Study Design Flowchart

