In the event the subject becomes lost to follow-up, the investigational site should make two documented attempts to contact the subject. A Study Exit record must be completed and the subject will no longer be followed in the clinical study.

Data Collection Overview

A review of patient files is required to determine preliminary eligibility according to patient inclusion and exclusion criteria. Baseline data including functional tests must be collected no more than **30** days prior to randomization. Baseline imaging such as echo and CT scans must be collected no more than 90 days prior to randomization. See the data collection table for details.

Follow-up data will be collected at the time of implant, hospital discharge, at planned follow-ups (6 week, 3, 6, 12, 18-month and annually from the implant date thereafter up to 5 years). All serious adverse events will be collected throughout the study until closure.

All study subjects will follow the prescribed follow-up scheduled despite randomization. Day 0 for the treatment group will be the day of implant. Day 0 for the Control Group will be the day of randomization. Each group will continue with optimal medical therapy for the duration of the study, including all standard of care medications and treatments including transplant, VAD, etc. If the subjects are transplanted or placed on another device they will be censored from the primary endpoint analysis and study exited. Subjects implanted with the C-Pulse will be followed until device removal. If the PIL is explanted and not replaced, the subject will be followed for safety until removal of the entire system.

Data will be collected via electronic data capture (EDC) screens referred to as e-case report forms (eCRFs). Echocardiogram tapes and digital storage media must be documented in the patient medical record for source documentation.

Table 1, below outlines the data collection with the appropriate follow-up time windows.

Table 1. Follow-up Windows

Evaluation	Time Window
Pre-Implant Evaluation	No more than 30 days prior to implant
Randomization	Post Baseline Testing and Pre-Implant
Implant	Day 0 (Treatment Group) – Implant Day 0 (Control Group) – Randomization
Pre-Discharge	Within 36 hours prior to discharge
6 – week follow-up	Days 42 ± 7 Post-Implant
3 – month follow-up	Days 90 ± 14 Post-Implant
6 – month follow-up	Days 180 ± 30 Post-Implant
12 – month follow-up	Day 365 ± 30 Post-Implant
18 – month follow-up	Day 540 ± 30 Post-Implant

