Report all associated adverse events. Update the device tracking records with all products. If the device is not returned to Sunshine Heart Inc., justification must be provided in the log.

Subject Withdrawal and Study Exit

A Study Exit record shall be completed if subject is unable to or refuses to continue participation in the study. Notify the Sunshine Heart clinical support team as soon as possible upon learning of a subject withdrawal/study exit.

If the subject fails to comply with follow-up visits, the study center must make repeated attempts to contact the subject. Each attempt to contact the subject must be documented in the subject's records and in the database.

If the subject officially withdraws from the study, the investigator will document the reason for withdrawal and indicate any relationship of the withdrawal to the study or the device on the eCRF.

If a subject withdraws from the study at any time, there will be no penalty or loss of future medical care.

STATISTICAL METHODS AND DATA ANALYSIS

Analysis Population

All randomized subjects will be included in the evaluation of the primary efficacy objective. Subjects will not be allowed to cross-over. All subjects implanted with the C-Pulse System will be included in the evaluation of the primary safety objective. In the event a randomized subject does not receive the implant or does not receive the randomized therapy, the subject will be analyzed according to the randomized assignment for the primary analyses. Additional supporting analyses of the primary efficacy endpoint will be conducted (as treated and per-protocol) which exclude subjects who do not receive the randomized treatment or those with major protocol deviations. The defined analysis cohorts are:

- Intent to treat: All randomized subject irrespective of treatment actually received (primary efficacy analysis)
- As treated: All randomized subjects receiving treatment as randomized
- Per protocol: All randomized subjects without major protocol deviations

Primary Efficacy Endpoint

The primary efficacy endpoint is defined as freedom from worsening heart failure related hospitalization, LVAD implant, heart transplant, and death.

The primary efficacy endpoint includes all occurrences of worsening heart failure events and will be analyzed utilizing a multiple failure time analysis.

Hypotheses

H_0 : HR=1,

H_A : HR \neq 1,

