The poolability of the primary efficacy endpoint across clinical sites will be assessed using a covariate adjusted proportional hazards regression model including an interaction term for clinical site and treatment group. In the event statistical evidence of a difference in treatment effect by site is found, an analysis utilizing a random effects model with a random effect for site will be conducted.

Type I Error Control for Secondary Objectives

The secondary efficacy objectives will be tested in a hierarchical fashion in the order listed only in the event the primary efficacy objective is met, thereby preserving an overall Type I error rate of 5%.

Handling of Missing Data

For the primary efficacy analysis, subjects lost to follow-up or explanted will be censored at the date of the last assessment.

Additional analyses of the follow-up assessments of KCCQ, six minute walk and LVEF will be conducted to assess the impact of missing data at month 12. The Wilcoxon Sign-Rank test with the worst rank imputed for data missing due to death, LVAD transplant, heart transplant or explant (in order of time to outcome) will be used to assess treatment differences in the continuous parameters while including subjects who withdrew from randomized treatment prior to the 12 month assessment. Multiple imputation analyses will be conducted to assess the robustness of the study results against data missing due to losses to follow-up and study non-compliance or un-interpretable test results.

Impact of Covariates on the Potential Treatment Differences

Additional exploratory statistical analyses of the primary and secondary study results will be conducted to assess for impact of selected baseline and follow-up parameters on the observed treatment differences. This will involve the stratification of results by categorical parameters and covariate adjusted regression analyses for the assessment of interaction with randomization assignment. Of particular interest will be an assessment for any treatment differences in the efficacy or safety parameters by gender. Other baseline covariates of interest will include classification based on race/ethnicity, age at implant, INTERMACS profile, NYHA, etiology (ischemic/non-ischemic), CRT/ICD therapy, angina, arrhythmia, hyperlipidemia and diabetes and the continuous covariates of baseline six-minute walk, KCCQ and MLWHF.

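### Follow-up of treatment-arm subjects who are anesthetized but not implanted ends at discharge or 30 days, although the primary efficacy analysis must include them as randomized; subjects never implanted also have no Day 0

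*Combined protocol and SAP*

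**What the plan says.** **Short follow-up (Study Description, Design).** The rule is triggered as follows: "If a subject undergoes anesthesia for the purpose of C-Pulse implantation but does not receive a C-Pulse System". In that case "the subject will be followed for 30 days for safety or until they are discharged, whichever occurs first". The same section gives 12 months as the minimum follow-up.

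**Time origin (Procedures, Data Collection Overview, and Table 1).** "Day 0 for the treatment group will be the day of implant", whereas "Day 0 for the Control Group will be the day of randomization". Every scheduled visit in Table 1 from 6 weeks on is counted from implant. The same section also states a general rule: "All study subjects will follow the prescribed follow-up scheduled despite randomization".

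**Analysis set (Statistical Methods and Data Analysis, Analysis Population).** "All randomized subjects will be included in the evaluation of the primary efficacy objective". For someone who does not get the implant, "the subject will be analyzed according to the randomized assignment for the primary analyses".

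**Censoring (Handling of Missing Data).** "For the primary efficacy analysis, subjects lost to follow-up or explanted will be censored at the date of the last assessment". A subject who never had a device has not been explanted, and one whose follow-up ends by protocol is not lost in the ordinary sense.

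**The concern.** An intent-to-treat analysis needs outcome data on everyone randomized. Here the analysis section keeps the abandoned-implant subject in the device arm, and the design section stops observing that subject within weeks. The subject is counted but contributes almost no time at risk.

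The loss falls on one arm only, because controls cannot have an abandoned implant. The subjects concerned have had anesthesia, and perhaps surgery, without receiving the therapy. If their outcomes resemble those of controls, or are worse, leaving them out hides the dilution that intent-to-treat is meant to show. Events not collected prospectively may not be recoverable later.

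A second and smaller gap concerns treatment subjects who never reach anesthesia, for example because they decline or miss the consent-to-implant window. The short-follow-up rule does not apply to them, but their visits cannot be dated.

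**Working it through.** **1. The plan's own figure.** Inputs from Primary Efficacy Endpoint Sample Size: control 6-month event-free proportion 0.72, HR 0.70, two-sided 0.05, power 0.80, accrual 2.5 years, minimum follow-up 12 months, attrition 10% per year, 1:1 allocation.

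- Control hazard λc = −2 ln(0.72) = 0.657 per year. Device hazard λt = 0.70 × 0.657 = 0.460. Loss hazard γ = −ln(0.9) = 0.105.
- Events (Schoenfeld): 4(1.960 + 0.842)² / (ln 0.70)² = 247.
- With uniform accrual and s = λ + γ, P(event) = (λ/s) × {1 − [exp(−s) − exp(−3.5s)] / (2.5s)}. This gives 0.682 for control and 0.566 for device, mean 0.624.
- N = 247 / 0.624 = 396, within 3% of the stated 388. The stated 265 events match what 388 subjects would yield with no attrition (265.8). Nothing below depends on that difference.

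**2. Number affected.** The documents give no non-implant rate. Assume q = 2%, 5% or 10% of 194: 3.9, 9.7 or 19.4 subjects.

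**3. First events lost if observation stops at 30 days, non-implanted subjects at control hazard.**

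- By day 30: 1 − exp(−0.657 × 30/365.25) = 0.0525.
- Over the trial: lost = 194q × (0.682 − 0.0525), which is 2.4, 6.1 and 12.2.
- Within 12 months, ignoring attrition: 1 − 0.72² = 0.4816, so lost = 194q × (0.4816 − 0.0525), which is 1.7, 4.2 and 8.3.
- Discharge before day 30 would make these slightly larger.

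**4. Effect on the estimate.** Device-arm rate = events / person-time, with person-time = events / hazard in each subgroup. At q = 10%:

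- Full follow-up: events 174.6 × 0.566 + 19.4 × 0.682 = 98.8 + 13.2 = 112.1; person-years 98.8/0.460 + 13.2/0.657 = 235.0; ratio (112.1/235.0)/0.657 = 0.726.
- 30-day stop: events 98.8 + 1.0 = 99.9; person-years 214.9 + 1.6 = 216.5; ratio 0.702.

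| Non-implanted | Ratio, full follow-up | Ratio, 30-day stop | Power, full | Power, 30-day stop |
|---|---|---|---|---|
| 2% | 0.705 | 0.700 | 77.7% | 78.8% |
| 5% | 0.713 | 0.701 | 75.2% | 78.1% |
| 10% | 0.726 | 0.702 | 70.8% | 76.9% |

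Power is Φ(√D × |ln HR| / 2 − 1.96), where D is the expected number of events. The value to which a Cox first-event estimate converges under the same assumptions agrees with the ratios to three decimals.

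**5. Higher risk.** If non-implanted subjects had twice the control hazard (an assumption with no source in the documents), the Cox limit with full follow-up is 0.714, 0.736 and 0.775 at 2%, 5% and 10%. With the 30-day stop it is 0.702 to 0.709.

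**The case against.** The strongest defence is that the 30-day rule is described as safety follow-up and does not mention study exit. Elsewhere the protocol says so explicitly when a subject is to leave. The general schedule rule and the 12-month minimum could then be read as still applying. This stands in part: exit is an inference. It remains the natural reading, because serious adverse events are already collected for everyone until study closure, so a 30-day safety limit has little meaning unless follow-up ends there. Neither general statement mentions the abandoned-implant case.

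A reader might infer that every treatment subject who is not implanted drops out of observation, so that the primary comparison becomes successfully implanted subjects against all controls. The documents do not support that. The short rule covers only subjects who had anesthesia. The rest stay under the general schedule and under serious adverse event collection, which includes serious events leading to hospital admission; their defect is the undefined Day 0.

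A reader might also infer a hazard ratio as high as 0.83, from the simple average 0.90 × 0.70 + 0.10 × 2. That overstates the first-event effect, because high-risk subjects have their event early and leave the risk set; the Cox limit is 0.775.

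The primary time origin and detailed methods are deferred to a Statistical Analysis Plan whose text is not in the document reviewed. It could settle censoring, but no analysis method recovers events that were not collected. For the 12-month walk, LVEF and KCCQ, Handling of Missing Data plans supplementary worst-rank and multiple-imputation analyses, which partly cover the missing values.

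Finally, subjects unfit for surgery or with unsuitable aortas are excluded at screening, so the affected number may be near the low end.

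**Conclusion.** The follow-up rule and the intent-to-treat rule conflict in current text, and the treatment-arm Day 0 is undefined for anyone not implanted. Followed as written, and reading the 30-day rule as the end of follow-up, the plan leaves primary endpoint events uncollected in one arm.

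The bias favours the device on the primary endpoint and is small at low rates. At control-level risk, the hazard ratio that full follow-up would show is higher by about 0.005 at 2% non-implanted and 0.024 at 10%. Doubled risk would widen the gap, to 0.775 against 0.709 at 10%. All of this rests on an assumed non-implant rate, constant hazards, and every affected subject falling under the 30-day rule, which is an upper case because the rule covers only those anesthetized.

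The direction may differ on days alive out of hospital. If the abandoned implant counts as study exit, that endpoint subtracts all days after exit: 365 − 30 = 335 days for an exit 30 days after randomization. The same subject could then be censored early in the primary analysis and heavily penalized in a secondary one, which is a further reason to reconcile the text.

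**What to change.** - **Design section:** state that anyone randomized to Treatment who does not receive a C-Pulse System, for whatever reason, stays in the study on the Control visit schedule with full collection of primary and secondary endpoints. Keep the 30-day period only as additional safety follow-up after an abandoned implant.
- **Data Collection Overview and Table 1:** set Day 0 for these subjects as the date of randomization.
- **Data collection table:** limit device-specific items, such as the device log and the gated 12-month CT, to implanted subjects.
- **Handling of Missing Data:** say that not being implanted is not in itself a reason for censoring.

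The cost is protocol wording and routine visits for a few subjects, who consent at entry to follow-up for five years. The estimate may be slightly less favourable to the device if non-implanted subjects do worse; that is the result an as-randomized analysis is meant to report.

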Patients will be enrolled into the trial upon providing informed consent. Each subject will be randomized after meeting the Eligibility Criteria and completion of baseline testing. Due to time required for baseline testing and scheduling of implant, sites will manage these items within the 30 day window as suited for the individual institution and patient. Procedures related directly to the study must not be performed prior to informed consent. Data collection will be noted prior to implantation of the device and at six months following implant, then long term at 12 and 18 months followed by annually post-implant for five years. Serious adverse events (SAE) will be collected throughout the study until study closure and will be adjudicated by an independent Clinical Event Committee (CEC).

Progress reports of the clinical outcomes will be reviewed by the DSMB after randomization of forty (40) patients and at least twice annually based on study progress. A progress report will be sent to FDA for review as specified in the Statistical Methods and Data Analysis section.

The total duration of the study including the enrollment and 12 month follow-up is expected to be approximately 36-42 months.

OBJECTIVES

Primary Objectives

The primary objectives of the study are to demonstrate the safety and efficacy of the C-Pulse therapy as compared to OMT. Refer to the section on Statistical Methods and Data Analysis for a detailed discussion of the definitions and methodology.

1. Primary Efficacy Objective:

To demonstrate the superiority of the C-Pulse therapy in increasing survival free from worsening heart failure resulting in hospitalization, LVAD implantation, cardiac transplantation or death as compared to OMT.

2. Primary Safety Objective:

To demonstrate the safety of the C-Pulse System by evaluating freedom from serious adverse events that are adjudicated as definitely related to device, therapy or procedure and resulting in either surgical intervention or death.

Secondary Objectives

The secondary objectives are as follows:

1. To demonstrate the superiority of C-Pulse therapy as compared to the OMT Control in improvement in 6 Minute Hall Walk score at 12 months post-randomization.
2. To demonstrate the superiority of C-Pulse therapy as compared to the OMT Control in improvement in 6 Minute Hall Walk score at 18 months post-randomization.

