The primary safety endpoint is 12 month freedom from serious adverse events that are adjudicated definitely related to device, therapy or procedure and resulting in either surgical intervention or death. All serious adverse events that are adjudicated by CEC to be definitely related to device, therapy or procedure and result in either surgical intervention or death will be included in the analysis. Events will be reported by number of event and proportion of subjects with event along with the ninety-five percent binomial exact confidence limits. Only first event counts towards the endpoint for each subject.

The proportion of C-Pulse[®] subjects free from serious adverse events that are adjudicated definitely related to device, therapy or procedure and result in surgical intervention or death through 12 months following implant and will be compared to the performance goal (PG) of 0.60.

The hypotheses are:

$$H_0: \Pi \leq PG,$$

$$H_A: \Pi > PG,$$

where Π is the 12 month freedom from serious adverse events that are definitely related to device, therapy or procedure and resulting in either surgical intervention or death and PG is the performance goal. If the lower, two-sided, 95% confidence bound is greater than 0.6 the objective will be met.

Primary Safety Endpoint Sample Size

Sample size was estimated for a combined freedom from serious adverse events adjudicated definitely related to device, therapy or procedure resulting in surgical intervention (to repair, replace or remove the implanted device) or death. The minimum required sample size and total number of device related deaths and device related surgical intervention events was calculated under the following assumptions:

- Significance level = 0.05
- Power = 0.80
- 12 month freedom from serious adverse events definitely related to device, therapy or procedure resulting in either surgical intervention (to repair, replace or remove implanted device) or death event of 70%.
- Minimum follow-up of 12 months

Under the above assumptions a minimum of 182 subjects are required.

Justification for Primary Safety Endpoint Sample Size

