The total days alive and out of hospital following randomization through 12 months will be computed for each subject. Each subject will contribute a maximum of 365 days alive and outside of hospital following randomization. Days the subject is in hospital will be subtracted from the maximum. For subjects with a death or study exit prior to 12 months, the days from the date of death or study exit to the date at 365 days post randomization will be subtracted from the total. The treatment groups will be compared under the following hypotheses.

Hypotheses:

$$H_0: DT = D_c$$

$$H_A: DT \neq D_c,$$

where DT represents the distribution of days alive and out of hospital for Treatment and D_c the distribution of days alive and out of hospital for Control. Details of the analysis methods can be found in the Statistical Analysis Plan.

6. Improvement in KCCQ Score at 12 months

The improvement in overall KCCQ score will be computed as the difference between the baseline and follow-up scores at 12 months. Subjects not evaluated at 12 months due to prior VAD implant, heart transplant or death will have the worst possible outcome imputed for improvement. Improvement at 12 months will be compared between treatment groups under the following hypotheses.

Hypotheses

$$H_0: DT = Dc$$

$$H_A: DT \neq Dc,$$

where DT represents the distribution of improvement in Overall KCCQ Score for Treatment and Dc the distribution of improvement in Overall KCCQ for Control. Details of the analysis methods can be found in the Statistical Analysis Plan.

Additional Supportive Analyses

1. Components of primary efficacy endpoint

The components of the primary endpoint will be summarized individually by treatment group. The proportions of subjects with heart failure related hospitalization, LVAD implant, heart transplant, and death due to worsening heart failure will be reported and the time to each event will be described by Kaplan-Meier curves. The number and proportion of subjects with hospitalization due to worsening heart failure as well as the rate per patient year will be summarized.

2. All-cause mortality

All-cause mortality will be summarized by treatment group by number and percent of subjects as well as by Kaplan-Meier curves.

3. Major cardiac events

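### The lead sentence on the primary objectives sets safety against OMT, but the safety test is single-arm against 0.60 and all-cause mortality has no between-arm estimate

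*Combined protocol and SAP*

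**What the plan says.** Under Objectives, Primary Objectives, the lead sentence reads "The primary objectives of the study are to demonstrate the safety and efficacy of the C-Pulse therapy as compared to OMT", and the reader is then sent to the statistical section for definitions and methods. Two numbered objectives follow. The efficacy objective ends with a comparison to OMT. The safety objective begins "To demonstrate the safety of the C-Pulse System by evaluating freedom from serious adverse events that are adjudicated as definitely related to device, therapy or" and names no comparator.

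Under Statistical Methods and Data Analysis, Analysis Population, "All subjects implanted with the C-Pulse System will be included in the evaluation of the primary safety objective". Under Primary Safety Endpoint, the 12-month event-free proportion "will be compared to the performance goal (PG) of 0.60", and the success rule is "If the lower, two-sided, 95% confidence bound is greater than 0.6 the objective will be met". On the interval method, "Events will be reported by number of event and proportion of subjects with event along with the ninety-five percent binomial exact confidence limits".

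Under Additional Supportive Analyses, item 2, "All-cause mortality will be summarized by treatment group by number and percent of subjects as well as by Kaplan-Meier curves". Unlike the primary efficacy and secondary endpoints, this item does not defer to the Statistical Analysis Plan for methods. Item 4 of the same list plans a Poisson regression of adverse event rates between arms, with 95% intervals for risk ratios.

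**The concern.** Read literally, the lead sentence promises a randomized safety comparison. The design cannot give one on the chosen endpoint. Events judged definitely related to the device, its therapy or the procedure essentially cannot occur in a subject who has no device, so there is nothing in the OMT arm to compare with.

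All-cause death needs no attribution and is observed in both arms. In a trial of thoracic surgery against continued medical therapy, it is the natural place to look for a cost of the intervention. The section Justification for the Investigation argues that benefit may exist even with equivalent survival, and it lists all-cause mortality among the endpoints of interest. Curves and percentages without an effect estimate and interval do not tell a reader which survival differences the data exclude.

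**Working it through.** **1. Is the sizing single-arm?** Inputs from Primary Safety Endpoint Sample Size: goal 0.60, assumed freedom 0.70, power 0.80, "Significance level = 0.05" (taken as two-sided).

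n = [(1.960 × √(0.6 × 0.4) + 0.842 × √(0.7 × 0.3)) / 0.10]² = [(0.960 + 0.386) / 0.10]² = 181.1, rounded up to 182. This is the protocol's figure, and no control-arm quantity enters it.

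**2. What does the success rule allow?** Using the exact (Clopper-Pearson) lower 2.5% limit:
- 182 implanted: 123 event-free gives a lower limit of 0.603, so up to 59 may have an event. Power at 0.70 is 0.787.
- 194 implanted: 131 event-free gives 0.604 and passes; 130 gives 0.599 and fails. Up to 63 (63/194 = 32.5%) may have an event. Type I error is 0.018 and power 0.798.

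The verdict is the same whatever is observed under OMT.

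**3. Where does death enter a between-arm analysis?**
- Primary efficacy composite: unqualified death in the endpoint definition, but death due to worsening heart failure in the component summary.
- Days alive and out of hospital (two secondary endpoints): mixed with hospital days and, in the all-hospitalization version, study exit.
- 6-minute walk, LVEF and KCCQ: as a worst-outcome imputation.
- Poisson regression: within adverse event rates.

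None isolates all-cause mortality.

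**4. How precise would a mortality estimate be?** Inputs: N = 388, uniform accrual over 2.5 years, data cut at 3.5 years and 10% loss per year (hazard l = −ln 0.90 = 0.105), following the efficacy sample-size assumptions. Constant hazards are assumed. Mortality hazard m:
- assumed 10% a year: 0.105;
- from the 84% six-month survival in the efficacy sample-size justification: −2 ln 0.84 = 0.349.

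With x the hazard of exit for transplant or another device, and h = m + l + x:

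deaths = 388 × (m/h) × [1 − (e^(−h) − e^(−3.5h)) / (2.5h)]; interval factor for the hazard ratio = exp(1.96 × 2/√deaths).

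The protocol gives no exit rate. As an assumption, x is 25% to 100% of the non-death hazard implied by the 64% and 84% six-month figures: −2 ln 0.64 − 0.349 = 0.544, so x = 0.136 to 0.544. The cited 64% composite includes inotrope use, so the upper end is generous.

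| Mortality | No such exits | x = 0.136 | x = 0.544 |
|---|---|---|---|
| 10% a year | 72 deaths, 1.59 | 62, 1.64 | 43, 1.82 |
| 84% alive at 6 months | 185, 1.33 | 163, 1.36 | 117, 1.44 |

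**5. 12-month risk difference.** Half-width = 1.96 × √(2p(1 − p)/194), ignoring censoring. At assumed mortality of 10%, 20% and 29.4% (the last is 1 − 0.84²) it is 6.0, 8.0 and 9.1 points. A non-inferiority test with an assumed 10-point margin (one-sided 0.025, 80% power) needs 142, 252 and 327 per arm; a 5-point margin needs 566, 1005 and 1305. With 194 per arm this is mostly out of reach.

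**The case against.** The wording fault is confined to one introductory sentence. The next sentence refers to the statistical section, the itemised safety objective names no comparator, and population, goal, hypotheses and success rule then agree with each other. All of this stands. A reader might infer that the safety objective itself is a comparison with OMT, or that meeting 0.60 will be reported as safety shown against OMT. The documents support neither: only the lead sentence links safety to OMT, and the protocol says only that the objective will be met.

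A reader might also infer that a mortality cost would go unseen between the arms. That is too strong, given the analyses in step 3 above. Days alive and out of hospital, in particular, is counted from randomization and tested in the secondary hierarchy. What remains is narrower: death appears only in mixtures.

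The strongest objection concerns the added estimate. Data Collection Overview exits subjects at transplant or another device and follows implanted subjects only until device removal. Later deaths are not collected, so censoring may be informative and may differ by arm. The estimate therefore cannot be presented as complete all-randomized mortality, and the death counts without exits are optimistic. This stands, and it is why the fix asks for disclosure and a count of exits.

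**Conclusion.** The lead sentence is wrong as written: the safety test is single-arm, and up to 63 of 194 implanted subjects (32.5%) may have a qualifying event with the objective still met, independent of the OMT arm. That count assumes all 194 are implanted and evaluable at 12 months under the exact limit.

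The missing mortality estimate is a cheap improvement, not an error that undermines the primary analyses. Its likely precision is a hazard-ratio interval factor between 1.33 and 1.59 with only 10% a year lost, or 1.36 to 1.82 once device and transplant exits are allowed for. Constant hazards, the mortality range and the exit rates are assumptions; only the 84% and 64% six-month figures come from the protocol. The trial is not sized for a mortality test and should not be read as one.

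**What to change.** 1. In Primary Objectives, limit the comparison with OMT to efficacy, and state that safety is tested in implanted subjects against the 0.60 performance goal.
2. In Additional Supportive Analyses, item 2, add a between-arm all-cause mortality estimate in all randomized subjects. Time it from randomization in both arms, because Day 0 is implant for treatment and randomization for control. Give the hazard ratio with 95% CI and the 12-month Kaplan-Meier risk difference with 95% CI. Report them beside the primary safety result, labelled as estimation.
3. With that estimate, state that deaths after exit for transplant, another device or device removal are not collected, that censoring may be informative, and give the number of such exits by arm.

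Cost: a wording edit and one supportive analysis, with no added subjects, visits or alpha. The downside is interpretive: under the present follow-up rules the estimate carries the censoring limitation above, which the added analysis does not remove.
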